³Screening laboratory tests include: white blood cell (WBC) count, platelet count, ALT, AST, and creatinine (and calculate an estimated glomerular filtration rate (eGFR) the formula used is determined by the sites, but should be consistent throughout the study), and pregnancy test. Laboratory tests performed in the 48 hours prior to enrollment will be accepted for determination of eligibility. See [Section 8.1.1](#) for more information about pregnancy tests in post-partum women.

⁴Baseline assessments should be performed prior to first study product administration. Results of Day 1 (baseline) laboratory assessment do not need to be reviewed to determine if initial study product should be given.

⁵Laboratory tests performed as part of routine clinical care in the 36 hours prior to first dose will be accepted for the baseline safety laboratory tests. Baseline may be the same as the screening laboratory tests.

⁶Safety laboratory tests include WBC count, differential, hemoglobin, platelet count, creatinine, total bilirubin, ALT, AST, INR, d-dimer, and C-reactive protein (CRP). Note: D-dimer and CRP values may predict severity and support assessment of outcomes and unlike other safety laboratory values, D-dimer and CRP should not be graded.

⁷Any laboratory tests performed as part of routine clinical care within the specified visit window can be used for safety laboratory testing.

⁸Daily until hospital discharge or end of study, whichever comes first. See [Section 8.1.2.1](#) for more information about doing an ordinal scale assessment on the day after hospital discharge and on the day after a subject dies.

⁹In-person visits are preferred but recognizing quarantine and other factors may limit the subject's ability to return to the site for the visit. In this case, the visit may be performed by phone call, home visit or remote telehealth procedure as per institutional standards. If subject is still hospitalized during the follow-up period, they should get Day 15, 22 and 29 assessments along with the daily clinical data collection.

- If still hospitalized at Day 15 and 29 or returns to the site for an in-person visit or home visit: collect clinical data, vital signs, safety laboratory tests, and research laboratory samples (OP swab and serum only) as able.
- If phone call or remote telehealth visit only on Days 15 and 29 and all Day 22 visits: assess adverse events, clinical status (ordinal scale), readmission to a hospital, and mortality only.

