Study subjects who qualify will be randomized in the Advantage eClinical system, and all others will be registered as screen failures. The ordinal scale and the NEWS should be done at the time of randomization; the site will need this data to randomize the subject in eClinical. The study team has 24 hours to complete other Day 1 baseline assessments prior to the first study product administration including the collection of OP swab and blood and completing or recording a baseline physical examination that was done. Clinical laboratory tests collected as part of routine care of the patients in the 36 hours prior to first dose qualify for baseline safety tests on Day1.

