3.3. Study Definitions and Derived Variables

3.3.1. Baseline Value

For efficacy assessments, the baseline value will be defined as the last value obtained prior to randomization. For safety assessments, the baseline value will be defined as the last value obtained prior to the first on-trial dose of any study product (interferon beta-1a, remdesivir, or placebo). If the exact time of the assessment or the first dose is not available, but collected on the same date, the assessment will be assumed to have occurred prior to receipt of study product.

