6.5. Missing Data

All attempts will be made to collect all data per protocol. Any data point that appears to be erroneous or inexplicable based on clinical judgment will be investigated as a possible outlier. If data points are identified as outliers, sensitivity analyses may be performed to examine the impact of including or excluding the outliers. Any substantive differences in these analyses will be reported.

For time to event outcomes, subjects who are lost to follow-up or terminate the study prior to Day 29 and prior to observing/experiencing the event will be censored at the time of their last observed assessment. Subjects who die prior to observing/experiencing the event will be censored at Day 29.

For the analysis of the key secondary outcome, subjects who are discharged but are subsequently re-admitted prior to Day 15 without a reported clinical score, their clinical score will be imputed at 7, which is the highest value for a hospitalized subject.

For the analyses of the secondary outcomes that involve clinical score (i.e. the key secondary outcome and time to improvement), if a subject is discharged from the hospital (but not to hospice or other end-of-life care) without a previously or concurrently reported clinical score of 1 or 2, then their clinical score at the time of discharge will be imputed as 2, which is the highest value for a non-hospitalized subject. If a subject terminates early from the study while they are

hospitalized or completes the study while still hospitalized, the last observed clinical score assessment will be used as their final assessment.

For the modified version of the ordinal score described in Section 4.3, if a subject is discharged from the hospital without a previously or concurrently reported clinical score of 2 or 3, then their clinical score at the time of discharge will be imputed as 3, which is the highest value for a non-hospitalized subject.

For the analyses of the secondary outcomes described in Section 3.3, the following imputation rules will be used for subjects who are lost to follow-up, terminate early from the study, or do not have further outcome data available after discharge for any reason:

- NEWS Total score (any missing study day)
 - If the subject dies or is discharged to hospice or other end-of-life care prior to the missing study day, the worst NEWS score (20) will be imputed

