- Lab Efficacy (d-dimer and CRP)
 - If results are not available for any visit day (s), but are available for visits before or after that visit, the average of the two nearest visits will be imputed for all missing visits between them. If a subject dies or is otherwise lost to follow-up, their last available observation will be carried forward. If baseline is missing, another pre-treatment dose will be used, or the earliest post-treatment dose will be used.

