	Day 29	Interferon + RDV	x	xx.x	xx.x, xx.x	xx.x	xx.x, xx.x	x	xx.x	xx.x, xx.x	xx.x	xx.x, xx.x
		Placebo + RDV	x	xx.x	xx.x, xx.x	xx.x	xx.x, xx.x	x	xx.x	xx.x, xx.x	xx.x	xx.x, xx.x
Continue for all parameters...												
N = Number of subjects in the As Treated Population with laboratory data available for the parameter at the specified study visit.												
High-sensitivity CRP values are excluded from the summaries.												

Table with similar format:

Table 46: Summary Statistics of Laboratory Efficacy Results by Parameter, Study Visit Day, and Treatment Group – mITT Population, Baseline Ordinal Score of 6

Programming notes for Table 45 and Table 46:

Use imputed results for missing data, see Section [6.5](#).

Table 47: Categorical Demographic and Baseline Characteristics by Baseline Ordinal Score and Treatment Group – mITT Population

Demographic Category	Characteristic	Interferon beta-1a + RDV						Placebo + RDV						All Subjects						All Subjects					
		Baseline OS 4 (N=X)		Baseline OS 5 (N=X)		Baseline OS 6 (N=X)		All Subjects (N=X)		Baseline OS 4 (N=X)		Baseline OS 5 (N=X)		Baseline OS 6 (N=X)		All Subjects (N=X)		Baseline OS 4 (N=X)		Baseline OS 5 (N=X)		Baseline OS 6 (N=X)		All Subjects (N=X)	
		n	%	n	%	n	%	n	%	n	%	n	%	n	%	n	%	n	%	n	%	n	%	n	%
Sex	Male	x	x	x	x	x	x	x	x	x	x	x	x	x	x	x	x	x	x	x	x	x	x	x	x
	Female	x	x	x	x	x	x	x	x	x	x	x	x	x	x	x	x	x	x	x	x	x	x	x	x
Ethnicity	Not Hispanic or Latino	x	x	x	x	x	x	x	x	x	x	x	x	x	x	x	x	x	x	x	x	x	x	x	x
	Hispanic or Latino	x	x	x	x	x	x	x	x	x	x	x	x	x	x	x	x	x	x	x	x	x	x	x	x
	Not Reported	x	x	x	x	x	x	x	x	x	x	x	x	x	x	x	x	x	x	x	x	x	x	x	x
	Unknown	x	x	x	x	x	x	x	x	x	x	x	x	x	x	x	x	x	x	x	x	x	x	x	x
Race	American Indian or Alaska Native	x	x	x	x	x	x	x	x	x	x	x	x	x	x	x	x	x	x	x	x	x	x	x	x
	Asian	x	x	x	x	x	x	x	x	x	x	x	x	x	x	x	x	x	x	x	x	x	x	x	x
	Native Hawaiian or Other Pacific Islander	x	x	x	x	x	x	x	x	x	x	x	x	x	x	x	x	x	x	x	x	x	x	x	x
	Black or African American	x	x	x	x	x	x	x	x	x	x	x	x	x	x	x	x	x	x	x	x	x	x	x	x
	White	x	x	x	x	x	x	x	x	x	x	x	x	x	x	x	x	x	x	x	x	x	x	x	x
	Multi-Racial	x	x	x	x	x	x	x	x	x	x	x	x	x	x	x	x	x	x	x	x	x	x	x	x
	Unknown	x	x	x	x	x	x	x	x	x	x	x	x	x	x	x	x	x	x	x	x	x	x	x	x
Geographic Region	Region 1	x	x	x	x	x	x	x	x	x	x	x	x	x	x	x	x	x	x	x	x	x	x	x	x
	...Continue for all region categorizations	x	x	x	x	x	x	x	x	x	x	x	x	x	x	x	x	x	x	x	x	x	x	x	x
Country	Country 1	x	x	x	x	x	x	x	x	x	x	x	x	x	x	x	x	x	x	x	x	x	x	x	x
	...Continue for all countries	x	x	x	x	x	x	x	x	x	x	x	x	x	x	x	x	x	x	x	x	x	x	x	x

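### SAP 6.5 lets a post-treatment d-dimer or CRP result stand in for a missing baseline, contrary to the SAP's own definition of baseline

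*SAP*

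**What the plan says.** SAP 3.3.1 fixes the baseline. For efficacy, "For efficacy assessments, the baseline value will be defined as the last value obtained prior to randomization". For safety it is the most recent result before dosing on the trial begins. One special case is given: where times are unknown but the date matches the first dose, "the assessment will be assumed to have occurred prior to receipt of study product". No other exception appears, and there is no pointer to 6.5.

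SAP 6.5, in its bullet on laboratory efficacy (d-dimer and CRP), adds: "If baseline is missing, another pre-treatment dose will be used, or the earliest post-treatment dose will be used". It does not mention 3.3.1. The bullet belongs to a list whose lead-in covers subjects who are lost, who leave early, "or do not have further outcome data available after discharge for any reason".

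In SAP Appendix 1, the programming notes for Tables 45 and 46 (baseline ordinal score 4 or 5, and 6) say "Use imputed results for missing data" and point to 6.5. The Table 45 layout, which Table 46 follows, has a Baseline row and change-from-baseline columns. Its footnote defines N as subjects "with laboratory data available for the parameter at the specified study visit".

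**The concern.** A baseline should be a value that treatment cannot have influenced. The first fallback in 6.5, another pre-treatment result, respects that. The second does not. Under Protocol Appendix C 1.2, injections are scheduled on Days 1 and 3 and the next laboratory draw is Day 3 ± 1, so the substitute may follow one or two injections. The protocol itself raises the possibility that interferon increased inflammation in category 6 subjects (Appendix C 1.1), who are the subjects of Table 46.

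At stake are the summary tables for two listed secondary efficacy markers. For affected subjects they would hold changes set by a rule instead of measured, and the Baseline row would mix pre-dose and post-dose results without telling the reader which are which.

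**Working it through.** **1. The two rules side by side.** No post-treatment value can meet either definition in SAP 3.3.1, yet 6.5 permits one. SAP 3.3.3 and 3.3.4 do refer forward to 6.5 when imputation is intended; 3.3.1 does not.

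**2. Can the fallback be reached?** Yes, though not often.
- Screening "tests include: white blood cell (WBC) count, platelet count, ALT, AST, and creatinine", plus a pregnancy test, so d-dimer and CRP are not screening tests. The Day 1 draw is their only scheduled pre-dose sample (Protocol Appendix C 1.2).
- SAP 4.3 drops high-sensitivity CRP results from one site, so a Day 1 value from that assay is lost.
- Working against this, routine-care results from the 36 hours before the first dose are accepted (Protocol Appendix C 1.2), and same-date samples of unknown time count as pre-dose (SAP 3.3.1).

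**3. Effect on the mean.** Let m be the share of an arm whose baseline comes from a post-treatment visit, and δ the true mean change up to that visit among them. For such a subject

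shown change at t = (Y_t − Y_0) − (Y_first − Y_0).

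The arm's Baseline row therefore moves by +mδ, and its mean change at the supplying visit and later moves by −mδ. The documents give neither m nor δ, so both are assumed:

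| m | shift in mean change, δ = −1.0 SD | shift in mean change, δ = +0.5 SD |
|---|---|---|
| 2% | +0.02 SD | −0.01 SD |
| 5% | +0.05 SD | −0.025 SD |
| 10% | +0.10 SD | −0.05 SD |

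A marker that falls early appears to fall less; one that rises early has its later change shifted downward. The direction depends on the marker's path.

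**4. Effect on the comparison between arms.**
- Equal m, and δ the same in affected as in other subjects of an arm: the arm difference in change at the supplying visit is (1 − m) times the true one, that is 98%, 95% or 90% at m = 2%, 5% or 10%.
- Unequal m and no treatment effect: a spurious difference of (difference in m) × |δ|. For 5% against 10% this is 0.05|δ|.

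**5. Effect on interval width at the supplying visit.** A share m has change exactly zero; the rest have mean μ. With an assumed baseline-to-post correlation of 0.7, the change variance is 2(1 − 0.7) = 0.6 in SD² units. Relative to complete data, the width ratio is √[(1 − m)(1 + mμ²/0.6)]. At m = 10%:
- μ = −0.5: √(0.9 × 1.0417) = 0.968
- μ = −1.0: √(0.9 × 1.1667) = 1.025
- μ = −1.5: √(0.9 × 1.375) = 1.112

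The interval may come out too narrow or too wide.

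**6. One subject.** Assume CRP of 120, 90, 70 and 50 at baseline and Days 3, 5 and 8.

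| Situation | Day 3 | Day 5 | Day 8 |
|---|---|---|---|
| True change | −30 | −50 | −70 |
| Baseline missing (90 used) | 0 | −20 | −40 |
| Baseline and Day 3 missing (70 used) | 0* | 0 | −20 |
| Only Day 3 observed, carried forward | 0 | 0 | 0 |

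*This entry assumes the imputed baseline of 70 is averaged with Day 5 (70) to fill Day 3. SAP 6.5 gives no order of operations. Averaging the two nearest observed visits, (70 + 50)/2 = 60, would give −10, and Day 3 could also be left unfilled.

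**The case against.** The strongest reply is that this is ordinary SAP structure: 3.3.1 defines baseline when a value exists, and 6.5, in plain sight, says what to do when it does not. That is fair as far as it goes. The rule is not hidden; it is only not identified as an exception. But a substitute that contradicts the definition's essential feature, being pre-treatment, is more than filling a gap.

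The lead-in to the 6.5 list is narrower than subjects with a missing baseline. It also refers to outcomes described in SAP 3.3, where d-dimer and CRP do not appear. On a strict reading the rule might seldom apply. However, the baseline sentence carries no such limit, and the note to Tables 45 and 46 refers to missing data without restriction. A programmer would apply it.

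If imputed values do not count towards the footnoted N, the number without an observed baseline could be inferred. Even then, the reader could not separate subjects given another pre-treatment result from those given a post-dose one.

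The size is wholly assumed. The Day 1 ± 1 window in the venipuncture tables (Protocol Appendix C 8.2) means the substitute could be drawn about a day after dosing, with δ near zero and almost no shift. That stands, as does the fact that the rule is the same in both arms and the tables carry no p-value or between-arm column. But if interferon moves the marker early, δ differs by arm, and that difference is what a reader of these tables is looking for.

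Finally, omission is also biased if a missing baseline is related to the marker's course. This stands, and is why the number omitted should be shown.

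**Conclusion.** The concern holds, as a minor correction worth making. SAP 6.5 allows a post-treatment baseline that 3.3.1 rules out, and Tables 45 and 46 are told to use it. For affected subjects, change is zero by construction at the supplying visit, and the arm's mean change shifts by −mδ from then on: 0.02 to 0.10 SD in size for m of 2% to 10% with δ = −1.0 SD, and half that, in the other direction, with δ = +0.5 SD. Both m and δ are assumptions, and m is probably small. The conclusion does not depend on the averaging example, which rests on an unstated imputation order.

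The reach is limited to descriptive laboratory summaries. The primary and main key secondary analyses are not affected. The covariate-adjusted models in Tables 12 and 18 are left outside this point, because the 6.5 bullet concerns laboratory outcomes, not covariates.

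**What to change.** Replace the baseline sentence in SAP 6.5 with:

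> If the 3.3.1 baseline (last value before randomization) is missing, the last value before the first dose of study product will be used; if none exists, baseline is missing and post-dose values are not used as baseline.

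The middle step openly departs from the efficacy definition in 3.3.1. It is needed because, once a subject is randomized, Protocol Appendix C 8.1.1 says "The study team has 24 hours to complete other Day 1 baseline assessments prior to the first study product administration", blood collection included, so a proper Day 1 sample can fall after randomization. State also that the sentence covers every subject without a baseline result, whatever the lead-in says.

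In Tables 45 and 46, omit subjects with no pre-dose value from the Baseline row and the change columns, keep their post-baseline absolute values, and footnote their number. With no imputed baseline, the question of whether it feeds the averaging rule also disappears.

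The cost is one sentence, one footnote and slightly fewer subjects in the change columns. Half-width relative to complete data is 1/√(1 − m): 1.010, 1.026 and 1.054 at m = 2%, 5% and 10%. Against the present rule at the supplying visit with m = 10%, 1.054 is wider than 0.968 and 1.025 but narrower than 1.112, depending on the mean change. Omission recovers the true mean change only if a missing baseline is unrelated to the marker's course.

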6.6. Interim Analyses and Data Monitoring

6.6.1. Planned Interim and Early Analyses

A DSMB will monitor ongoing results to ensure subject well-being and safety as well as study integrity. The DSMB will be asked to recommend early termination or modification only when there is clear and substantial evidence of a treatment difference.

On September 4, 2020, the DSMB met for an interim safety review of ACTT-3 data, and they recommended that DMID close further enrollment to patients with a baseline ordinal score of 6. Given that there are multiple clinical trials evaluating interferon beta for the treatment of COVID-19 worldwide, a public announcement describing the change in enrollment was made to inform the scientific community.

6.6.2. Interim Safety Review

Safety analyses will evaluate Grade 3 and 4 AE and SAEs by treatment arm. Safety monitoring will be ongoing with the DSMB reviewing safety data approximately every one to two weeks during the study. The unblinded statistical team will prepare these reports for review by the DSMB.

6.6.3. Interim Efficacy Review

An interim efficacy analysis will be conducted after approximately 50% of total information has been reached. The information fraction at an interim analysis will be computed as $t = r/723$ where r is the number of recoveries by the time of the data freeze date for the interim analysis. The Lan-DeMets spending function analog of the O'Brien-Fleming boundary will be used to monitor the primary endpoint using an overall two-sided type-I error rate of 0.05. Specifically, two one sided boundaries are constructed at level 0.025 using the spending function

$$\alpha^*(t) = 2[1 - \Phi\{2.241/t^{\frac{1}{2}}\}],$$

where Φ is the standard normal distribution function. Lan-DeMets software from the University of Wisconsin, now available in the R package 'ldbounds', will be used to calculate boundaries.

Conditional power will be presented as an additional guide to the DSMB. Conditional power allows computation of the probability of obtaining a statistically significant result by the end of the trial given the data accumulated thus far, incorporating and assuming a hypothesized treatment effect (e.g., the treatment effect assumed for sample size determination) thereafter. If conditional power is less than 20% under the original trial assumptions, consideration should be given to stopping the trial.

The unblinded statistical team will prepare these closed session reports for DSMB review and recommendations. Analyses will be presented with blinded codes for treatment arms to protect against the possibility that the DSMB report may fall into the wrong hands. A DSMB Charter will further describe procedures and membership.

6.7. Multicenter Studies

Data will be pooled across all clinical sites. Secondary analyses of the primary outcome will account for site via stratification by geographic region as noted in Section 6.4.

A sensitivity analysis of the primary outcome will be performed to assess the impact of individual sites on the observed treatment effect. Letting M be the total number of sites, the primary analysis will be repeated by excluding a single clinical site and performing the analyses on the remaining $M-1$ sites. This process will be repeated so that estimates are generated for each of the $M-1$ subset datasets. Presentations from these analyses are described in Section 8.1.2.

6.8. Multiple Comparisons/Multiplicity

There is only one primary outcome measure. The study utilizes a group-sequential design to control the overall type I error rate while allowing for formal interim analyses of the primary outcome measure (as described in Section 6.6 and Section 8.1). For the primary analysis of time to recovery, the stratified log-rank test will be performed in the efficacy analysis populations including all three severity strata and the p-value will be reported. If the resulting p-value is significant, then the analysis that excludes subjects in the severity = 6 strata will include the stratified log-rank test and the p-value will be reported. If the p-value from the primary analysis (including all three strata) is not significant, then the stratified log-rank test will not be performed for the analysis that excludes the severity = 6 strata and no p-value will be reported.

Likewise, the p-value for the analyses of the following will only be reported if the p-value from the primary analysis of time to recovery (including all three strata) is significant:

- The proportional odds model for the key secondary endpoint of clinical status score at Study Visit Day 15;
- Time to death through Day 15 (baseline ordinal score 4 or 5);
- Time to death through Day 29 (baseline ordinal score 4 or 5).

There is no planned adjustment for multiple comparisons in any secondary or exploratory analyses.

7. STUDY SUBJECTS

7.1. Disposition of Subjects

A summary of the reasons that subjects were screened but not randomized will be tabulated ([Table 1](#)).

The composition of analysis populations, including reasons for subject exclusion will be summarized by treatment group and disease severity ([Table 2](#)). A subject listing of subjects excluded from the As Treated Population will be generated ([Listing 1](#)).

The disposition of subjects will be tabulated by treatment group and randomized disease severity ([Table 3](#)). Study milestones included in the table will include, but not limited to: the total number of subjects that were randomized, completed expected blood draws, completed Study Day 15 visit, completed Study Day 22 visit, and completed Study Day 29 visit. For the calculation of percentages, subjects who die will not be included in the denominators for visits/assessments beyond their death. Subject status at study termination will be summarized by treatment group and baseline ordinal score ([Table 4](#)).

Treatment exposure will be summarized by treatment group ([Table 5](#) and [Table 6](#)). Summaries of prior remdesivir treatment by treatment group and baseline ordinal score will also be provided ([Table 7](#)).

A flowchart showing the disposition of study subjects, adapted from the Consort Statement [4] will be generated ([Figure 1](#)). This figure will present the number of subjects screened, randomized, lost to follow-up, and analyzed, by treatment group and baseline disease severity (ordinal scale 4, 5, or 6). The number of subjects that terminated early by hospitalization status at the time of the last ordinal score collection will be summarized graphically ([Figure 2](#)).

A listing of subjects who discontinued dosing or terminated study follow-up and the reason will be generated ([Listing 2](#)).

